## Sex Effects on Blood Pressure With Handgrip Training

### Research protocol

This study will be designed as a randomized, controlled, cross-over, repeated measures experiment. Fifty young healthy adult participants (25 males and 25 females) will visit the laboratory three times to perform a fatiguing bout of isometric handgrip exercise before and after both 4 weeks of isometric handgrip training and a no-exercise training condition. Participants will be randomly allocated to the isometric handgrip and the non-exercise training conditions using an online program (<http://www.randomizer.org/>). Participants that start with isometric handgrip training will return to the laboratory after a 4-wk washout, as this duration has been shown to decondition cardiovascular outcomes following training (1–3). To eliminate diurnal variation, each participant will visit the laboratory at the same time of day. Main outcomes in each visit will be measured at rest, during the fatiguing bout of isometric handgrip exercise, and 5, 10, 30, and 60-min post-exercise (see figure and Table 1). These measurement timings are aimed to characterize BP, and the cardiac autonomic and vascular function biphasic responses (4–6). Visits 2 and 3 will take place within 7 days of the last training session.

**Figure 1:** Experimental design, a randomized, controlled, cross-over, repeated measurements study. Abbreviations: CON; control, BRS baroreflex sensitivity, RMSSD, root mean square of

**Table 1** Procedures to be conducted in each visit to the laboratory

Procedures	Time (min)
Rest	15
Measurements	
1) BP, arterial stiffness, cardiac autonomic function	5
2) Brachial endothelial function (FMD)	15
Fatiguing isometric handgrip exercise	~ 3-5
Last isometric contraction	
Measurements	
1) BP, brachial blood flow	
2) Cardiac autonomic function (BRS, RMSSD, HF)	
Post 5 min	
Measurements	
1) BP, arterial stiffness (cfPWV), cardiac autonomic function (BRS, RMSSD, HF)	5
Post 10 min	
Measurements	
1) Brachial endothelial function (FMD)	15
Post 30 min	
Measurements	
1) BP, arterial stiffness (cfPWV), cardiac autonomic function (BRS, RMSSD, HF)	5
2) Brachial endothelial function (FMD)	15
Post 60 min	
Measurements	
1) BP, arterial stiffness (cfPWV), cardiac autonomic function	5
2) Brachial endothelial function (FMD)	15
	Total ~ 100

successive differences; HF, high-frequency power band; FMD; brachial artery flow-mediated dilation, cfPWV; central pulse wave velocity.

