### Sample size

Based upon an effect size of 0.160 and a drop-out rate of 15%, a priori power analysis (G-Power Version 3.1.9.3) for mixed ANOVA suggested a total of 50 participants are required to detect SBP mean differences of at least 5 mmHg over time and groups ( $\alpha = 0.05$ ,  $1-\beta=0.80$ ). Despite this mean difference obtained from a study that characterized BP responses after acute isometric handgrip exercise (7), we also aim to examine the effects of training on acute blood pressure responses to isometric handgrip exercise. Thus, given these differences in study design, we additionally set the effect size considering the small, standardized effect sizes ( $\leq 0.20$ ) for exercise training sciences (31).

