### Statistical analysis

Linear mixed models will be used to examine the effects of acute isometric handgrip exercise and training on BP, cardiac autonomic, and vascular function outcomes over time (i.e., aim 1, 2, and 3). These will be fitted with restricted maximum likelihood and applying Satterthwaite's method for approximating degrees of freedom for the F test using R lmerTest package (32). Fixed effects will be set as time, sex, training condition, and the random intercept as each participant. All models' residuals will be checked for normality and homogeneity of

variances using both Shapiro-Wilk and Levene tests, respectively, and through QQ plot inspection using the R performance package (33). Natural logarithm (Ln) transformations will be applied to HRV outcomes, as these are generally not normally distributed, but both transformed and untransformed data will be presented. Linear mixed models will be run with and without possible outliers identified through box plots as observations lying outside the 1.5 interquartile range. Unbiased effect sizes - partial omega squares ( $\omega^2$ ) will be estimated for each fixed effect and interactions terms and interpreted accordingly to the rough benchmarks set by Cohen (34) [small ( $\omega^2 < 0.05$ ), medium ( $\omega^2 < 0.25$ ), and large ( $\omega^2 > 0.25$ ) effects sizes]. Post-hoc comparisons will be performed using the Bonferroni correction, in the presence of significant fixed effects and interactions. MVC, %fat and free fat mass, and physical activity outcomes will be added to all linear mixed models as covariates, whereas resting HR and SRauc will be added to FMD and HRV main outcomes, respectively. In addition, the repeated measures correlation coefficient will be used to test associations between isometric handgrip exercise-induced BP changes before and after the training intervention and of BP with cardiac autonomic and vascular function outcomes (35). Multiple imputation procedures using full information maximum likelihood will only be used in case of a significant amount of missing data on outcomes (>15%) and if missing completely at random, as linear mixed modeling provides robust estimates for small to medium amounts of missingness (36). All statistical analyses will be conducted using R software, version 4.2.3 (37) with a significant level ( $\alpha$ ) of 0.05.

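### Adjusting every model for MVC, % fat and fat-free mass turns the sex main effect into a comparison of men and women of equal strength and body composition, and no model without these covariates is planned

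*Combined protocol and SAP*

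**What the plan says.** The title is "Sex Effects on Blood Pressure With Handgrip Training", and 25 men and 25 women are to be recruited. The Statistical analysis section uses linear mixed models "to examine the effects of acute isometric handgrip exercise and training on BP, cardiac autonomic, and vascular function outcomes over time". The model terms are given in one sentence: "Fixed effects will be set as time, sex, training condition, and the random intercept as each participant". Partial omega squared "will be estimated for each fixed effect and interactions terms", and significant fixed effects lead to Bonferroni-corrected post-hoc comparisons. The sex main effect will therefore be tested and sized for every outcome.

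The same section then states: "MVC, %fat and free fat mass, and physical activity outcomes will be added to all linear mixed models as covariates". It gives no reason for choosing them. The only comparison of models with and without something concerns outliers.

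Three things are left open: which interactions are fitted, whether the covariates are baseline or updated values, and whether they interact with time or condition. This matters most for MVC, which is measured at the baseline visit and again before each training session (Isometric handgrip training intervention and control).

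**The concern.** Grip strength, % fat and fat-free mass cannot confound sex in the usual sense, because they do not cause it; sex influences them. Conditioning on them changes the question from how men and women differ to how men and women differ when matched on strength and body composition. In a sample of 50, few participants may support that matched comparison. The covariates are also likely to be collinear with sex, which widens the confidence interval of the sex term.

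At stake is the reported sex difference in the level of BP, autonomic and vascular outcomes. A report that follows the plan could state no sex effect, or an exaggerated one, because of the adjustment set. The same shift enters any comparison of men with women at a single time point, since that comparison contains the sex coefficient.

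**Working it through.** **1. What the stated sample size supports.** The Sample size section cites an "a priori power analysis (G-Power Version 3.1.9.3) for mixed ANOVA" with effect size 0.160 (taken as Cohen's f), alpha 0.05, power 0.80 and 15% drop-out, giving 50. It does not name the test, the number of measurements m or their correlation ρ. In the G*Power formulation the noncentrality is f²·N·m/(1−ρ) for within and interaction tests, and f²·N·m/(1+(m−1)ρ) for a between-group test.
- Within or interaction test, 2 groups, m = 6, ρ = 0.5: 44 evaluable, and 44/0.85 = 51.8, so 52 enrolled. This is close to 50 but not a unique reproduction.
- Between-sex test, ρ = 0.5: 166 evaluable (m = 15) to 232 (m = 2).
- Power for a sex main effect at f = 0.16, before any covariate, with m from 4 to 12 and ρ from 0.5 to 0.7: 0.21–0.28 with 42 evaluable (50 × 0.85 = 42.5) and 0.24–0.33 with 50.

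So 50 fits a within or interaction test. The sex main effect has little power even before adjustment.

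**2. Standard error of the sex term.** With equal groups, R² of sex on the covariates is D²/(D²+4), so the variance inflation factor is 1 + D²/4 and the SE multiplier is its square root. D is the Mahalanobis male-female distance. Assume a within-sex correlation of 0.5 between MVC and fat-free mass, and % fat uncorrelated with both. Then D² = (a² + c² − ac)/0.75 + g², where a, c and g are the differences in MVC, fat-free mass and % fat in within-sex SD. All are assumptions.

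| a, c, g | D² | Inflation factor | SE multiplier |
|---|---|---|---|
| 1.0, 1.0, 0.8 | 1.97 | 1.49 | 1.22 |
| 1.5, 1.8, 1.2 | 5.16 | 2.29 | 1.51 |
| 2.0, 2.5, 1.5 | 9.25 | 3.31 | 1.82 |
| 2.5, 2.5, 1.5 | 10.58 | 3.65 | 1.91 |

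These multipliers ignore any fall in residual variance. In a simulation with 50 participants and mild separations, where the covariates carried the whole sex effect, the multiplier was only 1.06.

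**3. Direction of the change.** The adjusted coefficient is the total difference minus Σ(slope × male-female difference). Take a total of 0.8 residual SD and covariates explaining 15% of within-sex variance with slopes of equal size b. Then 4b² = 0.15/0.85, so b = 0.21. Men are higher on MVC and fat-free mass and lower on % fat.
- All slopes positive, differences 1.5/1.5/−1.0: 0.8 − 0.21 × 2.0 = 0.38. With 2.5/2.5/−1.5: 0.8 − 0.21 × 3.5 = 0.06.
- All slopes negative, 1.5/1.5/−1.0: 0.8 + 0.42 = 1.22.
- MVC and fat-free mass positive, % fat negative, 2.5/2.5/−1.5: 0.8 − 0.21 × 6.5 = −0.57. With all three signs switched: 0.8 + 1.37 = 2.17.

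Simulation with 21 per sex agrees. The unadjusted SE is 0.33; the adjusted SE is 0.46 at the smaller separation and 0.62–0.63 at the larger.

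**4. On the mmHg scale.** Assume 50 participants, a true sex difference of 5 mmHg, a between-person SD of 8 and a within-person SD of 5. The unadjusted estimate is 5.0 (SE 2.36, power about 0.54). If 0%, 50% or 100% of the difference runs through the covariates, the adjusted estimate is about 5.0, 2.4–2.6 or 0, with power 0.21–0.37, 0.09–0.15 or about 0.05.

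**5. Interactions.** In one simulated data set fitted by REML, the sex term was 7.49 (SE 2.47) without the covariates and 8.68 (SE 3.80) with them. Sex × condition was 1.088 (SE 1.898) in both. With an MVC that varied by condition it was 1.044 (SE 1.899).

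**The case against.** The strongest reply is that the trial's main sex question is untouched. The title speaks of sex effects with training, the models are described as examining exercise and training over time, and the sample size fits a within or interaction test. Additive covariates that are constant within a person leave sex-by-time and sex-by-training contrasts and their SEs unchanged. This stands, and it limits the point to the overall sex difference and to comparisons of men with women at one time. The protection would not be exact if MVC were updated after training, or if covariates interacted with time or condition. The plan is silent on both, although the one example with a varying MVC moved very little.

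A reader might infer that adjustment removes the sex effect for which the trial is named. The documents do not support that. The title points most naturally to the interactions, and the main effect disappears only if all of it runs through these covariates. With other slopes it grows or reverses, and the documents give no slopes. They give no male-female differences in MVC or body composition either, so every size above is conditional.

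Finally, asking whether a sex difference persists at equal strength and body composition is legitimate. That is so, but the plan does not pose this question and offers the conditional model as the only one.

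**Conclusion.** The point holds for the sex main effect. As written, the plan reports a conditional male-female difference without saying so and plans no estimate of the overall difference. The direction of the change cannot be known in advance. The SE is about 1.2 to 1.9 times larger under separations of about 1 to 2.5 within-sex SD in MVC and fat-free mass and 0.8 to 1.5 SD in % fat, all assumed. Because the test has low power before adjustment, a finding of no sex effect would be especially hard to read. Sex-by-time and sex-by-training contrasts stand if the covariates are time-constant and additive. The point deserves a change to the plan but does not undermine the trial's training question.

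**What to change.** - Take the sex main effect, its partial omega squared and any comparison of men with women at a single time point primarily from a model without MVC, % fat and fat-free mass.
- Report the model with these covariates as a labelled secondary, explanatory analysis of the difference at equal strength and body composition.
- Fix the covariates at their baseline values, and state that they enter as main effects only.

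Centring the covariates on each sex's own mean should not be used to claim a smaller SE for sex. The estimate then equals the unadjusted one, so its true sampling SD stays at 0.33–0.34, while the model reports 0.31. In 20,000 simulated data sets with 21 per sex and 15% of variance explained, the type I error at a nominal 0.05 was 0.068.

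The cost is a short addition to the Statistical analysis section and one additional model reported per outcome. No new data are needed.

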#### Study main outcomes

The main outcomes of this study are brachial BP (i.e., SBP and DBP), cardiac autonomic function (i.e., RMSSD, HF, and cardiac baroreflex sensitivity), and vascular function (i.e., flow-mediated dilation (FMD), and central pulse wave velocity (cfPWV)).

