### *Cardiac autonomic function*

We will place electrodes directly on the skin of each participant to obtain the ECG trace required to estimate both heart-rate variability and baroreflex sensitivity outcomes.

**Heart rate variability and baroreflex sensitivity:** R-R intervals will be sampled at 1000 Hz frequency to obtain digital R waves digital sequences using the single ECG lead module of PowerLab data acquisition system (ADInstruments, BellaVista, NSW, Australia). All data acquisition and offline analyses will be conducted following the standards of the Task Force of the European Society of Cardiology and the North American Society of Pacing and Electrophysiology (17). Offline heart rate variability (HRV) analyses will be performed over a 2-min time series for each time-point (i.e., baseline, during and 5, 30 and 60 min after exercise) using the HRV analysis module of Lab Chart 8 (ADInstruments, BellaVista, NSW, Australia) (18). Main time-domain indices of interest include the standard deviation of NN intervals (SDNN) – a measure of overall variability, and the root mean square of the sum of the squares of the differences between NN intervals (RMSSD) – a measure of cardiovagal modulation. In addition, non-linear time-domain parameters will be derived from the Poincaré plot, including the vertical deviation that reflects mainly cardiovagal modulation (SD1), the longitudinal deviation (SD2), and the non-linear ratio SD1/SD2 an index of autonomic balance analogous to LF/HF ratio (19). The time-frequency domain analysis will be conducted using the Lomb-Scargle Periodogram, which permits accurate estimation of low (0.04 to 0.15 Hz) and high-power frequency (HF) power bands (0.15 to 0.40 Hz) in absolute and normalized power units during exercise conditions. Cardiac baroreflex sensitivity (BRS) will be estimated via the spontaneous sequence method over 2 min through the Lab Chart 8 baroreflex macro. Briefly, this method identifies ramps where increases in SBP ( $> 1$  mmHg) are coupled with increases of the RR interval ( $> 4$  ms) (linearly correlated) that occur over at least 3 beats (minimum sequence). The minimum acceptable correlation coefficient between SBP and RR interval ramps will be 0.80. Then, baroreflex sensitivity is estimated as the average of all regression slopes between the SBP and RR interval.

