### *Vascular function*

During the vascular function measurements, we will ask participants to lie quietly in the supine position. They will also experience a forearm occlusion to permit the assessment of endothelial function.

**Endothelial function:** will be non-invasively assessed via brachial artery FMD, which represents nitric oxide-dependent vasodilation and closely correlates with the endothelial function of the coronary arteries (20,21). FMD will be assessed in the right brachial artery with an ultrasound (Arietta V750, Fujifilm, Tokyo, Japan) equipped with a 7.5-MHz linear array probe incorporating a 5-MHz Doppler transducer, placed  $\sim 4$  cm above the antecubital fossa, and held by a stereotactic clamp following standard guidelines (22,23). Reactive hyperemia will be induced by rapid cuff deflation following a forearm occlusion (Hokanson SC10, Bellevue, WA 98005, USA) maintained for 5-min at 250 mmHg. Changes in intraluminal brachial artery diameter will be tracked with automated edge-detection software (FMD studio, Quipu srl, Pisa, Italy) allowing precise measurement of the artery diameter (23). Doppler measurements of peak hyperemic blood velocity with an insonation angle of  $\leq 60^\circ$  will allow calculation of FMD main stimuli - shear rate as  $(4 \times \text{peak blood velocity} / D_{\text{baseline}})$  (23). All FMD analyses will be done offline using the FMD studio. FMD will be presented both as an absolute change ( $\text{FMD (mm)} = D_{\text{peak}} - D_{\text{baseline}}$ ) and as a relative change ( $\% \text{ FMD} = (D_{\text{peak}} - D_{\text{bas}}/D_{\text{baseline}}) \times 100$ ) in diameter. If a non-linear ratio between  $D_{\text{peak}}$  and  $D_{\text{bas}}$

is observed (B coefficients < 1), %FMD will be allometrically scaled for  $D_{baseline}$  (24,25). In addition, blood flow will be estimated as (Mean blood velocity) x (Brachial Cross-Sectional Area) x (60). Brachial artery blood flow will be measured in both exercising and non-exercising arms. All FMD scans will be conducted by the same researcher with inter-day measurements CV <15% (22,23).

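### As written, the covariate rule gives resting HR to the FMD models and SRauc to the HRV models, against the protocol's own measurement sections; SRauc is undefined, and the plan does not say which MVC or physical activity value is used

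*Combined protocol and SAP*

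**What the plan says.** The Statistical analysis section sets two covariate rules for the linear mixed models.

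- For every model: "MVC, %fat and free fat mass, and physical activity outcomes will be added to all linear mixed models as covariates".
- For particular outcomes: "whereas resting HR and SR auc will be added to FMD and HRV main outcomes, respectively".

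The measurement sections describe where these variables come from.

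- **Shear rate.** Under Vascular function, Doppler measurements of peak hyperaemic velocity "will allow calculation of FMD main stimuli - shear rate as" 4 × peak blood velocity / baseline diameter.
- **HRV.** Under Cardiac autonomic function, "R-R intervals will be sampled at 1000 Hz frequency" from a single ECG lead. HRV indices are computed from that series.
- **MVC.** It is measured at the baseline visit (Baseline visit section) and again before every home session (Isometric handgrip training intervention and control). The Post-intervention visits section repeats the same bout but does not say explicitly that MVC is re-measured.
- **Physical activity.** The IPAQ is given at phone screening (Recruitment methods). The ambulatory blood pressure device also carries activity sensors (24-hour ambulatory BP).
- **Body composition.** The Bod Pod test is described under Body composition without a visit, and it is not in Table 1.

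**The concern.** The word that closes the second rule fixes the pairing: first covariate to first outcome, second to second. That sends resting heart rate to FMD and SRauc to HRV. An analyst who follows the text would leave FMD unadjusted for the quantity the protocol names as its stimulus, and would adjust RMSSD and HF for a brachial artery measure that the documents nowhere connect to them. An analyst who silently swaps the two would depart from the written plan on main outcomes. Either way the text and the analysis would disagree.

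Correcting the order does not make the rule usable, because SRauc has no definition. An area under the curve needs a start and an end, and the plan gives neither.

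The all-model covariates raise a smaller question. MVC is measured repeatedly while participants train. Training may change an MVC taken after it starts, and adjusting for such a value could remove part of the training effect that the model is meant to estimate.

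**Working it through.** The plan gives no figure to reproduce here. The check sets the sections side by side and counts the outcomes affected.

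**1. Pairing.**

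| Covariate | Outcome as written | What the measurement sections support |
|---|---|---|
| Resting HR | FMD | HRV, by inference: both come from the ECG |
| SRauc | HRV | FMD, explicitly: shear is named as its stimulus |

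The second row is a direct conflict within the document. The first row is weaker, since no section says that resting heart rate belongs with HRV. It follows from the shared signal, and from the fact that once SRauc goes to FMD, HRV is the outcome left for resting heart rate.

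**2. Outcomes affected.** Study main outcomes names SBP, DBP, RMSSD, HF, baroreflex sensitivity, FMD and cfPWV, which makes 7. The sentence reaches FMD (1) and the HRV outcomes RMSSD and HF (2), so 1 + 2 = 3 of 7. SBP, DBP and cfPWV are not mentioned in it, and the sample size calculation uses no covariates.

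**3. Definition of SRauc.** The term occurs once, in the sentence at issue. The only shear quantity defined is 4 × peak blood velocity / baseline diameter. This is a single peak value with no integration and no window, so SRauc cannot be computed from the plan.

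**4. Which value of the all-model covariates.**

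| Covariate | Occasions or sources in the protocol | Chosen in the analysis section? |
|---|---|---|
| MVC | Baseline visit; before each training session; possibly visits 2 and 3 | No |
| Physical activity | IPAQ at phone screening; sensors in the ambulatory device, no visit named | No |
| Body composition | Bod Pod, no visit named | No |

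For MVC the choice bears on the result. The baseline-visit value precedes both study conditions for every participant and is one number per person, so training cannot have altered it. A value taken after training begins lacks that protection.

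**The case against.** The strongest reply is that this is a slip of word order that any competent analyst would notice, because the measurement sections point the other way. That is probably true. It is a reason to correct the sentence, since the alternative is an undocumented departure from the plan on main outcomes. It also limits the weight of the point: nothing in the documents shows that any estimate would be biased by a given amount.

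The reply is also right that the link between resting heart rate and HRV is inferred. Only the link between shear and FMD is stated.

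A reader might infer more than the documents support in four places.

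- **No visit is named for MVC or physical activity.** This is not so. MVC has the baseline visit and each training session, and the IPAQ has phone screening. What is missing is the choice among them. Only body composition has no occasion at all.
- **Four of seven outcomes are affected, counting baroreflex sensitivity.** The Cardiac autonomic function section treats HRV and baroreflex sensitivity as two kinds of outcome, and Study main outcomes lists the latter as its own item. Three is the supported count.
- **The literal rule would lose HRV data.** HRV is analysed "for each time-point (i.e., baseline, during and 5, 30 and 60 min after exercise"), and Table 1 has no FMD scan during the bout or at 5 min. That would be 50 × 3 × 2 = 300 of 50 × 3 × 5 = 750 records. The loss needs SRauc to be matched by exact time and incomplete rows to be deleted, and the plan states neither. With one resting SRauc per visit the loss is 0.
- **Visit 1 resting heart rate, or FMD models with and without shear, are required.** These are defensible options, but correcting the error does not depend on them.

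**Conclusion.** The point holds in three parts. First, the outcome-specific covariate rule is wrong as written for 3 of the 7 named main outcomes (FMD, RMSSD, HF). Confidence is high that the text conflicts with the protocol's own account of shear and FMD; the other half of the pairing rests on the shared ECG source. Second, SRauc is undefined, so the rule cannot be carried out in either order. Third, the analysis section does not say which available MVC or physical activity value is used, and body composition has no stated visit.

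The size of any effect on the estimates cannot be derived from the documents. Absorption of the training effect by MVC is conditional on a value measured after training starts being used. This should be fixed before analysis; it does not call the design into question.

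**What to change.** Replace the outcome-specific rule with: *SRauc of the same scan will be added to the FMD models and resting HR to the HRV models.* If the present pairing is intended, justify it instead.

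Then either define SRauc with its formula and integration window, or replace it with the peak shear rate already given under Vascular function.

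Add one timing statement: MVC enters as the baseline-visit value; the physical activity covariate comes from a named source (IPAQ or device sensors) on a named occasion; and the Bod Pod test takes place at a named visit.

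The cost is one corrected sentence, one definition and one timing statement. The sample size does not change.

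### The planned repeated-measures correlation has no term for time point or visit, so with the exercise point included the shared rest-exercise-recovery curve alone can make it significant, and it cannot answer a between-person before/after-training question

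*Combined protocol and SAP*

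**What the plan says.** The Statistical analysis section gives the repeated-measures correlation two uses. In the first, "the repeated measures correlation coefficient will be used to test associations between isometric handgrip exercise-induced BP changes before and after the training intervention". The second follows directly: "and of BP with cardiac autonomic and vascular function outcomes". The section does not say which observations form a pair, whether visits are pooled, or whether the question is within or between persons.

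Time is modelled elsewhere. For the linear mixed models, "Fixed effects will be set as time, sex, training condition, and the random intercept as each participant". No such term is stated for the correlation.

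The Research protocol section has the main outcomes "measured at rest, during the fatiguing bout of isometric handgrip exercise, and 5, 10, 30, and 60-min post-exercise", at times "aimed to characterize BP, and the cardiac autonomic and vascular function biphasic responses". Heart rate variability is analysed at five points ("i.e., baseline, during and 5, 30 and 60 min after exercise"). Table 1 lists BP, brachial blood flow and autonomic measures at the last contraction, but neither FMD nor cfPWV there.

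**The concern.** A repeated-measures correlation subtracts each participant's mean from both variables and correlates what is left. It leaves the average time course in. Two variables that both move with exercise will then correlate because everyone exercised, even if a person's BP deviation says nothing about that person's autonomic deviation. The plan itself expects a time course in all three outcome families.

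The before/after-training use has a second difficulty. Whether people with a larger acute BP response before training also have a larger one afterwards is most naturally a question between persons, and this coefficient discards all between-person variation.

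At stake is the reading of the only association tests in this section. A significant coefficient could be taken as a link between individual BP and autonomic responses, or as stability of individual BP responses, when it shows neither.

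**Working it through.** The documents give no figure for this correlation, so there is nothing to reproduce first.

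**Inputs from the documents.** There are 50 participants with 15% drop-out: 50 × 0.85 = 42.5, taken as 42. Alpha is 0.05. BP and autonomic measures share five times: rest, during exercise, and 5, 30 and 60 min.

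**Assumptions.** The plan gives no curve sizes and no within-person SD. I took SBP SDs of 6 to 11 mmHg. The upper value comes from the Sample size section if its effect size is read as Cohen's f for two groups: total SD = (5/2)/0.160 = 15.6 mmHg. With an assumed within-person correlation of 0.5, the within-person SD is 15.6 × √0.5 = 11.0.

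**Expected coefficient with no individual link.** For mean curves x and y over k points, centred on their own means, with independent errors:

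r ≈ Σxy / √{[Σx² + (k−1)σx²] [Σy² + (k−1)σy²]}, with df = n(k−1) − 1.

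**BP with an autonomic index, exercise point included.** Take SBP changes of 0, 20, −2, −5, −3 mmHg (SD 11) and lnRMSSD changes of 0, −0.3, 0.05, 0.05, 0 (SD 0.4).
- Σx² = 418, Σy² = 0.087, Σxy = −5.95.
- r ≈ −5.95 / √[(418 + 484)(0.087 + 0.64)] = −5.95 / 25.6 = −0.23.
- df = 42 × 4 − 1 = 167, so t ≈ −3.1. Simulation rejects in about 87% of trials, and in 5.2% once time-point means are also removed.

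The assumed range (SBP rise 10-30 mmHg, autonomic shift 0.3-1.0 SD) has these ends:
- Rise 10, shift 0.3 SD, SBP SD 11: r ≈ −2.4 / √(564 × 4.072) = −0.05, rejection about 10%.
- Rise 30, shift 1.0 SD, SBP SD 6: r ≈ −24 / √(864 × 4.8) = −0.37, rejection about 100%.

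Pooling visits makes it worse. With a 10 mmHg rise, an lnRMSSD drop of 0.3 and SD 11, rejection goes from 54% with one visit to 92% with three. The sign can also reverse: a true within-person r of +0.30 with opposed curves is estimated at −0.20, and at +0.30 after time-centring.

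**BP before and after training, exercise point included.** Take the same curve at both visits (0, 10, −2, −3, −2 mmHg) with independent deviations. Σx² = 115.2.
- SD 11: r ≈ 115.2 / (115.2 + 484) = 0.19, rejection 73%.
- SD 6: r ≈ 115.2 / (115.2 + 144) = 0.44, rejection 100%.
- Rise of 25 mmHg: rejection 100% at either SD.
- Time-centred: about 5% throughout.

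Using changes from rest is no cure. Within one visit, and with the rest point kept, raw values and changes give the same coefficient, because subtracting a constant per person is undone by the centring.

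**Exercise point left out (rest, 5, 30, 60 min).**
- BP-autonomic: with SBP 0, −2, −5, −3 and lnRMSSD 0, −0.1, 0.05, 0 at SD 11 and 0.4, r ≈ −0.175 / √(376 × 0.492) = −0.01. Rejection across settings is about 4-8%.
- Pre/post BP: 5-12% for falls of 2-3 mmHg, and about 10-40% for a fall of about 5 mmHg (SD 11 down to 6).

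**BP with vascular outcomes (no exercise point in Table 1).** Rejection ran from 8% to 71% for cfPWV and from 6% to 90% for FMD. The assumed curves and the pooling of visits decide where in those ranges it falls.

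**Between-person information.** With a true between-person correlation of 0.6 and no within-person link, the repeated-measures correlation rejects about 5% of the time and a person-level correlation about 95%. With one change per person and visit, k = 1 and df = 42 × 0 − 1 = −1, so the coefficient cannot be computed.

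**The case against.** The strongest reply is that the plan never assigns the exercise point to this test. Study main outcomes names brachial BP, and the Blood pressure section takes cuff readings only before and after exercise; during exercise BP comes from the finger device. On a recovery-only reading most of the inflation goes. That stands as a limit on the size. It does not remove the concern, because the Research protocol text and Table 1 schedule BP during exercise, the autonomic section does the same for its outcomes, and the correlation excludes nothing.

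A second reply is that covariation across rest, exercise and recovery is itself a within-person association. That is fair. It is misleading only if read as a link between individual responses, and blindness to between-person links is a fault only if that is the question. The plan leaves both open, which is why the question must be stated.

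A reader might infer more than the documents support:
- **That raw time points will be correlated.** The pairs are not defined, and the first use speaks of changes.
- **That spurious BP-vascular associations are certain.** FMD and cfPWV have no exercise measurement, and the result depends on assumed curves.
- **That false rejection is near certain throughout.** The BP-autonomic range starts at about 10%.
- **That the study's aims rest on this test.** Aims 1 to 3 are assigned to the mixed models, which include time; the correlation is an addition.

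**Conclusion.** The concern holds for a secondary analysis and should be fixed. With the exercise point included, 42 completers and no individual link, false rejection is about 10-100% for BP-autonomic pairs and about 73-100% for pre/post-training BP curves, against about 5% after time-centring. These ranges rest on assumed curves, SDs and independent errors, since the documents supply none. Recovery-only data make the BP-autonomic problem negligible, and make the pre/post problem small unless the fall in BP is about 5 mmHg. BP-vascular pairs can be affected, by an amount that cannot be fixed from the documents. For a between-person before/after question the coefficient is either uninformative or, with one change per visit, not computable. The mixed-model analyses are untouched.

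**What to change.** In the Statistical analysis section:
- State which observations are paired, whether the during-exercise point and which visits are included, and whether each question is within or between persons.
- For BP with autonomic or vascular outcomes, include time point and visit/condition as factors, so that residuals are correlated after removing participant means and time-by-visit means, with degrees of freedom reduced to match.
- For the before/after-training question, pre-specify one acute BP change per person and visit, and name the visit that counts as before training. Report a sex-adjusted person-level correlation with its confidence interval.

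No new data are needed, only a few sentences and a few lines of code. The reported correlations will be smaller, and the person-level one imprecise. By Fisher's z, the smallest |r| with 80% power is tanh[(1.96 + 0.84)/√(n − 3)], which is 0.39 for n = 50 and 0.42 for n = 42. A single change per visit also sets aside the other time points, so the choice should be justified in advance.
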